9.5.1. Baseline Characteristics and Demographics

Demographic variables (eg, age, sex, race, ethnicity, height, weight, and BMI) and Baseline characteristics will be summarized by injection group and overall.

Summary statistics (mean and standard deviation for continuous variables, and number and percentage for categorical variables) will be provided.

9.5.2. Immunogenicity Analyses

The analyses of immunogenicity will be based on the PPS. If the number of participants in the FAS and PPS differ (defined as the difference divided by the total number of participants in the PPS) by more than 10%, supportive analyses of immunogenicity may be conducted using the FAS. All immunogenicity analyses will be provided by study arm, at each timepoint unless otherwise specified.

For the immunogenicity endpoints, the GM of antibody titers as measured by HAI assay with corresponding 95% CI at each timepoint will be provided by study arm. The GMFR of antibody titers as measured by HAI assay with corresponding 95% CI at each postdose timepoint over predose (D1) will be provided by study arm. The 95% CIs will be calculated based on the t-distribution of the log-transformed values and then back-transformed to the original scale. Descriptive summary statistics, including median, minimum, and maximum will also be provided. For calculation of GMTs reported as below the LLOQ will be replaced by $0.5 \times \text{LLOQ}$. Values that are greater than the ULOQ will be converted to the ULOQ.

Vaccine seroresponse rate will be provided with a 2-sided 95% CI using the Clopper-Pearson method by study arm. Vaccine seroresponse is defined as an increase of neutralizing antibody titers from predose below the LLOQ to $\geq 4 \times \text{LLOQ}$ or at least a 4-fold rise if predose is $\geq \text{LLOQ}$. The number and percentage of participants with >2-, 3-fold increases from Baseline (if $\geq \text{LLOQ}$) or with >2-, 3-fold increases from LLOQ (if $< \text{LLOQ}$) will also be analyzed with 2-sided 95% CI using the Clopper-Pearson method by study arm, at each postdose timepoint. Further details will be described in the SAP.

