9.4. Analysis Sets

Analysis sets are listed in [Table 5](#).

Table 5: Analysis Sets

Participant Analysis Set	Description
Randomization Analysis Set	The Randomization Analysis Set consists of all participants who are randomized.
FAS	The FAS consists of all randomized participants who receive the study intervention. Participants will be included in the study arm to which the participant is randomized.
PPS for Immunogenicity	The PPS consists of all participants in the FAS who comply with the injection schedule, comply with the timing of immunogenicity blood sampling to have a Baseline (D1) and at least 1 postinjection assessment, and have no major protocol deviations which impact the immune response. The PPS will be used as the primary analysis set for analyses of immunogenicity unless otherwise specified.
Safety Set	Safety Set consists of all participants who receive one dose of study intervention. The Safety Set will be used for all analyses of safety except for the solicited ARs. Participants will be included in the study arm corresponding to the study intervention that they actually received.
Solicited Safety Set	The Solicited Safety Set consists of all participants in the Safety Set who contribute any solicited AR data. The Solicited Safety Set will be used for the analyses of solicited ARs. Participants will be included in the treatment group corresponding to the study intervention that they actually received.

Abbreviation: AR=adverse reaction; D=day; FAS=full analysis set; PPS=per protocol set.

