## 4. Study Design

### 4.1. Overall Study Design

This will be a randomized, observer-blind, Phase 2 study to evaluate the safety, reactogenicity and immunogenicity of mRNA-1010 vaccine candidate variations using a systems biology approach in healthy adults 18 to 49 years of age.

Three mRNA-1010 vaccine candidate versions will be evaluated:

- mRNA-1010: CCI
- 
- 
- 
- 
- 
- 
- 
- 
- 
- 
- 
- 
- 
- 
- 
- 
- 
- 
- 
- 
- 
- 
- 
- 
- 
- 
- 
- 
- 
- 
- 
- 
- 
- 
- 
- 
- 
- 
- 
- 
- 
- 
- 
- 
- 
- 
- 
- 
- 
- 
- 
- 
- 
- 
- 
- 
- 
- 
- 
- 
- 
- 
- 
- 
- 
- 
- 
- 
- 
- 
- 
- 
- 
- 
- 
- 
- 
- 
- 
- 
- 
- 
- 
- 
- 
- 
- 
- 
- 
- 
- 
- 
- 
- 
- 
- 
- 
- 
- 
- 
- 
- 
- 
- 
- 
- 
- 
- 
- 
- 
- 
- 
- 
- 
- 
- 
- 
- 
- 
- 
- 
- 
- 
- 
- 
- 
- 
- 
- 
- 
- 
- 
- 
- 
- 
- 
- 
- 
- 
- 
- 
- 
- 
- 
- 
- 
- 
- 
- 
- 
- 
- 
- 
- 
- 
- 
- 
- 
- 
- 
- 
- 
- 
- 
- 
- 
- 
- 
- 
- 
- 
- 
- 
- 
- 
- 
- 
- 
- 
- 
- 
- 
- 
- 
- 
- 
- 
- 
- 
- 
- 
- 
- 
- 
- 
- 
- 
- 
- 
- 
- 
- 
- 
- 
- 
- 
- 
- 
- 
- 
- 
- 
- 
- 
- 
- 
- 
- 
- 
- 
- 
- 
- 
- 
- 
- 
- 
- 
- 
- 
- 
- 
- 
- 
- 
- 
- 
- 
- 
- 
- 
- 
- 
- 
- 
- 
- 
- 
- 
- 
- 
- 
- 
- 
- 
- 
- 
- 
- 
- 
- 
- 
- 
- 
- 
- 
- 
- 
- 
- 
- 
- 
- 
- 
- 
- 
- 
- 
- 
- 
- 
- 
- 
- 
- 
- 
- 
- 
- 
- 
- 
- 
- 
- 
- 
- 
- 
- 
- 
- 
- 
- 
- 
- 
- 
- 
- 
- 
- 
- 
- 
- 
- 
- 
- 
- 
- 
- 
- 
- 
- 
- 
- 
- 
- 
- 
- 
- 
- 
- 
- 
- 
- 
- 
- 
- 
- 
- 
- 
- 
- 
- 
- 
- 
- 
- 
- 
- 
- 
- 
- 
- 
- 
- 
- 
- 
- 
- 
- 
- 
- 
- 
- 
- 
- 
- 
- 
- 
- 
- 
- 
- 
- 
- 
- 
- 
- [figure not shown] 150\%$  of the randomized vaccine product dose level will exclude a participant from the PP set based on the following rule ('Y' indicates exclusion):

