## 6.2. Background Characteristics

### 6.2.1. Participant Disposition

The number and percentage of participants in the following categories will be summarized by treatment group as defined in [Section 6.1](#) based on Randomization Set:

- Randomization Set
- Solicited Safety Set
- Safety Set
- Full Analysis Set
- Per-Protocol Set

The percentage will be based on participants in the Randomization Set.

The number of participants in the following categories will be summarized:

- Participants screened
- Screen failure participants
- Individual reasons for screen failure

The percentage of participants who screen failed will be based on the number of participants screened. The percentage of participants reporting each reason for screen failure will be based on the number of participants who screen failed.

The number and percentage of participants in each of the following disposition categories will be summarized overall and by treatment group based on the Randomization Set:

- Received study vaccine
- Completed study

- Prematurely discontinued the study and the reason for discontinuation

The number and percentage of participants will be summarized by site based on Randomization Set.

A participant disposition listing will be provided, including informed consent, participants who received study vaccine, participants who completed study, participants who discontinued from participation in the study, with reasons for discontinuation. A separate listing will be provided for screen failure participants with reasons for screen failure.

In addition, randomized participants with any inclusion and exclusion criteria violation will also be provided in a listing.

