### **6.2.2. Demographics**

Descriptive statistics will be calculated for the following continuous demographic and baseline characteristics: age (years), weight (kg), height (cm), and body mass index (BMI) ( $\text{kg}/\text{m}^2$ ). Number and percentage of participants will be provided for categorical variables such as gender, race, ethnicity, and age. The summaries will be presented by overall and treatment group based on the Safety Set, FAS, and PPS.

For screened failure participants, age (years), as well as gender, race, ethnicity will be presented in a listing.

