### **6.2.6. Important Protocol Deviations**

Important protocol deviations are a subset of protocol deviations that may significantly impact the completeness, accuracy, or reliability of the study data or that may significantly affect a participant's rights, safety, or well-being. Important protocol deviations rules will be developed and finalized before database lock.

The number and percentage of the participants with each important protocol deviation type will be provided by treatment group and overall based on the Randomization Set.

Important protocol deviations may impact immune response corresponding to the immunogenicity objective, and participants with such deviations will be excluded from the Per-Protocol Set for immunogenicity analyses; these important protocol deviations will be determined and documented by Sponsor prior to DBL and unblinding. Reasons of exclusion from Per-Protocol Set will be summarized and listed.

Important protocol deviations will be presented in a listing.

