## 6.4. Immunogenicity Analysis

The analysis of immunogenicity will be analyzed by vaccination group based on the PPS. If the number of participants in the FAS and PPS differ (defined as the difference divided by the total number of participants in the PPS by more than 10%), supportive analyses of immunogenicity may be conducted using the FAS. Supportive analysis is required if the condition is met at end of study; it is optional for the IA.

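### Does the pooled 10% trigger for supportive FAS immunogenicity results leave by-arm results unprotected?

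*Protocol*

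**What the plan says.** The per-protocol set (PPS) is the primary set for immunogenicity. Under Protocol 9.5.2, FAS results may be added when "the FAS and PPS differ (defined as the difference divided by the total number of participants in the PPS) by more than 10" percent. SAP 6.4 uses the same ratio and threshold and adds: "Supportive analysis is required if the condition is met at end of study; it is optional for the IA". Neither document applies the ratio within an arm.

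Reporting is by arm. Protocol 9.5.2 states: "All immunogenicity analyses will be provided by study arm, at each timepoint unless otherwise specified". Protocol Table 4 plans arms of 60, 30, 60, 30, 30 and 60, which sum to 270.

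Other places bear on what a reader would see:

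- SAP 6.2.1, on the sizes of the analysis sets, FAS and PPS included: "The number and percentage of participants in the following categories will be summarized by treatment group as defined in" SAP 6.1.
- SAP 6.2.2, on demographics: "The summaries will be presented by overall and treatment group based on the Safety Set, FAS, and PPS".
- SAP 6.2.6: "Reasons of exclusion from Per-Protocol Set will be summarized and listed".
- SAP 6.2.5 lists dosing errors, and the final study report includes individual unblinded listings (Protocol 9.6.2; SAP 6.5).

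**The concern.** The trigger decides whether FAS titers must be shown beside the PPS titers, and it looks at the wrong level for results that are read arm by arm. A 30-participant arm carries only a ninth of the total. It could lose a quarter or more of its members while the pooled ratio stays under 10%. That arm's geometric mean titer (GMT), geometric mean fold rise (GMFR) and seroresponse rate would then rest on a selected subset, with no guaranteed table showing how they change when the excluded participants return. In a dose-ranging study the arm summaries are the immunogenicity result.

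There is also a route by which losses could gather in one arm. Dosing errors are judged against the assigned dose: the rule just before SAP Table 2 says that a received dose outside a set percentage "of the randomized vaccine product dose level will exclude a participant from the PP set".

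**Working it through.** **Inputs.** Arm sizes come from Protocol Table 4, the ratio and 10% threshold from Protocol 9.5.2 and SAP 6.4. Assumptions: the FAS holds all 270, exclusions are independent between participants, and the pooled reading of the ratio is correct. The documents state no expected exclusion rate, so every rate below is assumed.

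**Where the rule fires.** With x exclusions the ratio is x/(270 − x).

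- x = 24: 24/246 = 9.76%, no trigger.
- x = 25: 25/245 = 10.2%, trigger.

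**What it can miss.**

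- 6 of 30 in one arm plus 12 of 240 elsewhere: 18/252 = 7.1% pooled, 6/24 = 25% in that arm.
- 8 of 30 in one arm plus 8 of 240 elsewhere: 16/254 = 6.3% pooled, 8/22 = 36% in that arm.

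Both patterns are possible. The question is how likely they are.

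**Common exclusion rate p in all arms.** An arm ratio of 25% or more means at least 6 of 30 or at least 12 of 60. The probability that the total is 24 or fewer and at least one arm reaches that level, computed exactly from three Bin(30, p) and three Bin(60, p) counts, is:

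| p | Rule silent, some arm at 25% or more |
|---|---|
| 3% | 0.07% |
| 5% | 0.95% |
| 8% | 3.7% |
| 10% | 2.2% |

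For a single named arm of 30, six or more exclusions at a 5% rate has probability P(Bin(30, 0.05) ≥ 6) = 0.3%.

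**One arm forced to 20%.** With Bin(30, 0.20) in that arm and Bin(240, r) elsewhere, the rule fires with probability 0.3% at r = 3.3%, 5.8% at r = 5% and 55% at r = 8%. The rule is weak when one arm is far worse than the rest and the rest lose few. This result depends on the 20%, which is an assumption with no source in the documents.

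**Is the same rule by arm better?** It would fire at 3 of 30 (3/27 = 11.1%) or 6 of 60 (6/54 = 11.1%). At a common 5% rate it fires by chance with probability 1 − [P(Bin(30, 0.05) ≤ 2)]³ × [P(Bin(60, 0.05) ≤ 5)]³ = 1 − 0.812³ × 0.921³ = 58%. The pooled rule fires with probability P(Bin(270, 0.05) ≥ 25) = 0.2%. In small arms a 10% threshold mostly detects noise, which is a sound reason to pool.

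**What an FAS run would add.** Not every excluded participant brings data back.

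- PPS membership needs a baseline and at least one postinjection sample (Protocol Table 5), and missing results are not imputed (SAP 6.1). A participant without a baseline adds nothing to GMFR or seroresponse; one without any postdose sample adds nothing after dosing.
- SAP 6.4.2 removes data collected after intercurrent events from the summaries, whichever set is used.
- For dosing errors the FAS keeps the assigned arm: "Participants will be included in the study arm to which the participant is randomized". Returning misdosed participants to that arm does not clarify its titers.

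**The case for a change.** The strongest case for the concern is that the by-arm tables show who was lost and why, but not how that arm's titers respond. In the readable text, nothing else guarantees that comparison below the trigger. An FAS run is permitted without the trigger, but one chosen after seeing unblinded by-arm losses would be post hoc, whereas showing both sets unconditionally would take a sentence or two and a rerun of existing programs.

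That much is true, and it would be a reasonable preference. It does not show that the chosen rule is wrong. A screen for whether a second population is worth running may be pooled even when results are by arm, and the by-arm version performs worse.

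The clustering argument also carries little weight. Patterns like those shown would need roughly 20% to 27% of one arm to be misdosed (6/30 and 8/30) if dosing error were the cause. This is a single injection prepared by designated unblinded staff, with receipt of the entire dose confirmed (Protocol 6.5 and 9.1). Other exclusion types have no stated reason to differ by arm in a randomized, observer-blind trial.

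One loose end is separate: SAP 6.4.2 and SAP Table 3 do not spell out how every intercurrent event is handled in an FAS run. That is a detail left open and does not bear on where the trigger is set.

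**Conclusion.** The concern does not hold. Protocol 9.5.2 and SAP 6.4 give the same ratio and threshold, and the SAP strengthens the consequence. Following the rule produces no incorrect GMT, GMFR or seroresponse rate; at most, one supportive descriptive table is not compulsory in an unlikely configuration. Under a common exclusion rate of 3% to 10% that configuration has probability 0.1% to 3.7%. It becomes likely only if one arm is assumed to run far above the others, for which the documents give neither a rate nor a convincing cause. If it did happen, the by-arm counts, demographics, exclusion reasons and listings would reveal it.

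The stakes are small: immunogenicity is secondary, and Protocol 9.2 rules out formal hypothesis tests, so neither type I error nor power is involved. The conclusion rests on the pooled reading, an FAS of 270, independent exclusions and assumed rates. Parts of the SAP on analysis sets and on immunogenicity comparisons cannot be read, so the absence of any further by-arm safeguard cannot be established either.

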9.5.3. Safety Analyses

All safety analyses will be based on the Safety Set, except summaries of solicited ARs, which will be based on the Solicited Safety Set. All safety analyses will be provided by vaccination group. Participants will be included in the study group corresponding to the study intervention that they actually received.

Safety and reactogenicity will be assessed by clinical review of all relevant parameters including solicited ARs (local and systemic ARs), unsolicited AEs (including any clinically significant safety laboratory abnormalities), treatment-related AEs, severe AEs, SAEs, MAAEs, AESIs, and AEs leading to withdrawal from study participation.

The number and percentage of participants with any solicited local AR, with any solicited systemic AR, with any solicited AR during the 7-day follow-up period after vaccination, and with Grade 3 or higher solicited AR will be provided. A 2-sided 95% exact CI using the

Clopper-Pearson method will be provided for the percentage of participants with any solicited AR.

The number and percentage of participants with unsolicited AEs, treatment-related AEs, severe AEs, SAEs, MAAEs, AESIs, and AEs leading to withdrawal from study participation will be summarized. Unsolicited AEs will be presented by MedDRA system organ class and preferred term. Unsolicited AEs will be coded according to the MedDRA Dictionary for Adverse Reaction Terminology.

The number of events of solicited ARs, unsolicited AEs, SAEs, MAAEs, and AESIs will be reported in summary tables accordingly.

9.5.4. Exploratory Analyses

CCI [REDACTED]
[REDACTED]
[REDACTED]
[REDACTED]
[REDACTED]
[REDACTED]
[REDACTED]

9.6. Planned Analyses

There will be at least one IA and a final CSR for this study.

9.6.1. Interim Analysis

CCI [REDACTED]
[REDACTED]
[REDACTED]

9.6.2. Final Clinical Study Report

The final CSR will include full unblinded analyses of all safety and immunogenicity with individual unblinded listings through EoS.

10. SUPPORTING DOCUMENTATION AND OPERATIONAL CONSIDERATIONS

10.1. Appendix 1: Regulatory, Ethical, and Study Oversight Considerations

10.1.1. Regulatory and Ethical Considerations

- This study will be conducted in accordance with the protocol and with the following:
 - Consensus ethical principles derived from international guidelines including the Declaration of Helsinki and Council for International Organizations of Medical Sciences international ethical guidelines.
 - Applicable ICH GCP guidelines.
 - Applicable laws and regulations.
- The protocol, protocol amendments, ICF, IB, and other relevant documents (eg, advertisements) must be submitted to an IRB/IEC by the Investigator and reviewed and approved by the IRB/IEC before the study is initiated.
- Any amendments to the protocol will require IRB/IEC approval before implementation of changes made to the study design, except for changes necessary to eliminate an immediate hazard to study participants.
- Protocols and any substantial amendments to the protocol will require health authority approval prior to initiation except for changes necessary to eliminate an immediate hazard to study participants.
- The Investigator will be responsible for the following, as applicable:
 - Providing written summaries of the status of the study to the IRB/IEC annually or more frequently in accordance with the requirements, policies, and procedures established by the IRB/IEC.
 - Notifying the IRB/IEC of SAEs or other significant safety findings as required by IRB/IEC procedures.
 - Providing oversight of the conduct of the study at the site and adherence to requirements of 21 CFR, ICH guidelines, the IRB/IEC, European regulation 536/2014 for clinical studies, and all other applicable local regulations.

10.1.2. Financial Disclosure

The Investigator is required to provide financial disclosure information to allow the Sponsor to submit the complete and accurate certification or disclosure statements required under 21 CFR 54. In addition, the Investigator must provide the Sponsor with a commitment to promptly update this information if any relevant changes occur during the course of the investigation and for 1 year after completion of the study.

The Sponsor, the CRO, and the study site are not financially responsible for further testing or treatment of any medical condition that may be detected during the screening process. In

addition, in the absence of specific arrangements, the Sponsor, the CRO, and the study site are not financially responsible for further treatment of the disease under study.

10.1.3. Informed Consent Process

- The Investigator or the Investigator's representative will explain the nature of the study, including the risks and benefits, to the potential participant and answer all questions regarding the study.
- Potential participants must be informed that their participation is voluntary. They will be required to sign a statement of informed consent that meets the requirements of 21 CFR 50, local regulations, ICH guidelines, privacy and data protection requirements, where applicable, and the IRB/IEC or study center.
- The medical record must include a statement that written informed consent was obtained before the participant was enrolled in the study and the date the written consent was obtained. The authorized person obtaining the informed consent must also sign the ICF.
- Participants must be re-consented to the most current version of the ICF(s) during their participation in the study.
- A copy of the ICF(s) must be provided to the participant.

A participant who is rescreened is not required to sign another ICF if the rescreening occurs within 28 days from the previous ICF signature date.

The ICF will contain a separate section that addresses the use of remaining mandatory samples for optional exploratory research. The Investigator or authorized designee will explain to each participant the objectives of the exploratory research. Participants will be told that they are free to refuse to participate and may withdraw their consent at any time and for any reason during the storage period. The ICF will require the participant to clearly indicate whether or not the participant agrees to allow any remaining specimens to be used for exploratory research.

10.1.4. Recruitment Strategy

Enrollment targets will be established to ensure the participant population reflects those that are most at risk for the condition, or those that are most reflective of the general population, if appropriate.

Participant recruitment and retention initiatives will be incorporated into the trial. These include, but are not limited to, services that provide a means to identify potential participants and direct them to participating clinical trial sites, participant support services such as concierge, and trial information and support collateral for both the participant and the site. Advertisements to be used for the recruitment of study participants, and any other written information regarding this study to be provided to the participant should be submitted to the Sponsor for approval. All documents must be approved by the IRB/IEC.

10.1.5. Data Protection

- Participants will be assigned a unique identifier by the Sponsor. Any participant records or datasets that are transferred to the Sponsor will contain the identifier only;

- participant names or any information which would make the participant identifiable will not be transferred.
- The participant must be informed that their personal study-related data will be used by the Sponsor in accordance with local data protection law. The level of disclosure must also be explained to the participant who will be required to give consent for their data to be used as described in the informed consent.
 - The participant must be informed that their medical records may be examined by Clinical Quality Assurance auditors or other authorized personnel appointed by the Sponsor, by appropriate IRB/IEC members and by inspectors from regulatory authorities.
 - The contract between the Sponsor or designee and the study sites may specify responsibilities of the parties related to data protection, including handling of data security breaches and respective communication and cooperation of the parties.
 - Information technology systems used to collect, process, and store study-related data are secured by technical and organizational security measures designed to protect such data against accidental or unlawful loss, alteration, or unauthorized disclosure or access.

